#### **6.12.6. Clinical Laboratory Evaluation**

Laboratory analyses will include planned analytes only. Planned analytes are those specified in the protocol (See Protocol Appendix 2). However, unscheduled measurements of planned analytes will be included/excluded as specified in the relevant sections. Examples of unplanned measurements include those that the clinical investigator orders as a repeat test or “retest” of a laboratory test in case of an abnormal value, and those the investigator orders for a “follow-up visit” due to clinical concerns. Some planned analytes are intended for individual case reviews and will not be included in group-level summaries.

#### **6.12.7. Vital Signs and Other Physical Findings**

The planned summaries are provided in [Table PYAD.6.9](#). The measurements analyzed for vital signs and physical characteristics include systolic blood pressure (BP), diastolic BP, pulse, weight, and temperature.

The criteria for identifying subjects with treatment-emergent abnormalities are based on [Table PYAD.6.10](#).

Some of the analyses of vital signs may be incorporated into interactive display tools instead of or in addition to a static display. Any display described in [Table PYAD.6.9](#) and not provided would be available upon request. For example, box plots for observed values, scatter plots, and shift tables could be provided as interactive displays for medical review.

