Additional manageable risks associated with most therapeutic monoclonal antibodies are the potential for infusion-related hypersensitivity and cytokine release reactions. The single infusion in this study will be administered at a controlled rate, the study participants will be monitored closely, and adjustments in the infusion rate will be made and/or the infusion stopped, if indicated. Additional information regarding infusion reaction management options is located in Section 6.1.1.2. As of 31 December 2020, approximately 4012 participants received blinded treatment of LY3819253 700 mg, 2800 mg, or 7000 mg, or placebo, of which approximately 3189 participants received LY3819253. Serious infusion-related reactions, including events consistent with anaphylaxis, were reported in these ongoing studies with LY3819253 (FDA EUA fact sheet 2020).

Clinical worsening of COVID-19 after administration of LY3819253 has been reported from post-authorization treatment within 24 hours of infusion. Signs and symptoms may include fever, hypoxia or increased respiratory difficulty, arrhythmia (e.g., atrial fibrillation, sinus tachycardia, and bradycardia), fatigue, and altered mental status. Some of these events required hospitalization. It is not known if these events were related to LY3819253 use or were due to progression of COVID-19.

Combination of LY3819253 and LY3832479

As of 04 November 2020, 542 participants in Study PYAB received blinded treatment of either placebo or the combination of 2800 mg LY3819253 and 2800 mg LY3832479. Three participants reported single immediate non-serious events of pruritis (2 events) and dyspnea (1 event).

Data from Study PYAB interim analysis indicate treatment with LY3819253 or the combination of LY3819253 and LY3832479 may decrease the risk of hospitalization in patients with mild to moderate COVID-19 (Chen et al. 2020; Gottlieb et al. 2020) thus providing benefit to patients with COVID-19.

Given the totality of data on LY3819253 and LY3832479, the well-established safety profile of other therapeutic mAbs, and the lack of disease directed therapeutic options for patients with COVID-19 illness or to prevent the SARS-CoV-2 infection, the overall benefit/risk assessment of this study is considered favorable.

More detailed information about the known and expected benefits and risks and reasonably expected adverse events of LY3819253 and LY3832479 may be found in each respective IB.

3. Objectives and Endpoints

Part 1

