8.2.2. Vital Signs

Vital signs will be measured at rest as specified in the SoA. Vital signs include

- body temperature
- blood pressure

- pulse rate
- respiration rate
- saturation of peripheral oxygen, and
- supplemental oxygen flow rate, FiO₂ if known, and method of delivery, if applicable.

If available during the study, optional remote vital status monitoring may be used to obtain vital data.

Additional vital signs may be measured during the study if warranted, as determined by the investigator.

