8.3.6. Hypersensitivity Reactions

Biologic agents carry the risk of systemic hypersensitivity reactions.

If such a reaction occurs, additional details describing each symptom should be provided to the sponsor in the infusion-related reaction/hypersensitivity CRF.

If symptoms and/or signs occur during or within 6 hours after infusion of LY3819253 and are believed to be hypersensitivity or due to cytokine release, then investigators are encouraged to

report the event as infusion-related immediate hypersensitivity reaction or cytokine release-associated infusion reaction, respectively.

Sites should have appropriately trained medical staff and appropriate medical equipment available when study participants are receiving intervention. It is recommended that participants who experience a systemic hypersensitivity reaction be treated per the local standard of care.

In the case of generalized urticaria or anaphylaxis, additional blood and urine samples should be collected as described in Section 10.6, Appendix 6, "Recommended Laboratory Testing for Hypersensitivity Events". Laboratory results are provided to the sponsor via the central laboratory.

In case of skin lesions or rash consistent with vasculitis, efforts should be made to perform the following as soon as possible

- dermatology consultation
- skin biopsy, and
- photographs of lesions of interest, including skin biopsy site.

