**Table PYAD.6.9. Tables and Figures Produced to Support Vital Signs and Physical Characteristics**

Analysis Type	Analysis Details
Box plots for observed values by visit	
 
Includes participants who have both a baseline and a postbaseline measurement from a planned visit.
 
Unplanned measurements will be excluded.
 
Last baseline will be used.
 
Descriptive summary statistics will be included in a table below the box plot.
 
No inferential statistics.
 

Box plots for change from baseline values by visit	
 
Includes participants who have both a baseline and a postbaseline planned measurement.
 
Unplanned measurements will be excluded.
 
Last baseline will be used.
 
Descriptive summary statistics will be included in a table below the box plot.
 
Change from last baseline to last postbaseline will also be summarized within the box plot of changes (rightmost column), and descriptive summary statistics will be included in a table below the box plot along with a p-value using the ANCOVA model.
 

Scatter plots of baseline-by-maximum values and baseline-by-minimum values	
 
Each study individually and studies combined will be displayed.
 
Includes participants who have both a baseline and postbaseline observation.
 
Unplanned measurements will be included.
 
Lines indicating the reference limits will be included.
 
Max vs Max: Maximum baseline versus maximum postbaseline.
 
Min vs Min: Minimum baseline versus minimum postbaseline.
 

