Summary tables for shifts to high/low	
 
Limits provided by the central lab service will be used to define low and high.
 
Normal/high to low: Includes the number and percentage of participants by treatment whose minimum baseline result is normal or high and whose minimum postbaseline result is low. 
 
Denominator equals participants whose minimum baseline result is normal or high and who have at least 1 postbaseline result.
 
 
 
Normal/low to high: Includes the number and percentage of participants by treatment whose maximum baseline result is normal or low and whose maximum postbaseline result is high. 
 
Denominator equals participants whose maximum baseline result is normal or low and who have at least 1 result during the treatment period.
 
 
 
Statistical comparisons will be included.
 

Abbreviations: ANCOVA = anaylsis of covariance; Max = maximum; Min = minimum.

**Table PYAD.6.10. Categorical Criteria for Abnormal Treatment-Emergent Blood Pressure and Pulse Measurement, and Categorical Criteria for Weight and Temperature Changes in Adults**

Parameter	Low	High
Systolic BP (mm Hg) (Supine or sitting – forearm at heart level)	$\leq 90$ and decrease from baseline $\geq 20$	$\geq 129$ and increase from baseline $\geq 20$
Diastolic BP (mm Hg) (Supine or sitting – forearm at heart level)	$\leq 50$ and decrease from baseline $\geq 10$	$\geq 90$ and increase from baseline $\geq 10$
Pulse (bpm) (Supine or sitting)	$<50$ and decrease from baseline $\geq 15$	$>100$ and increase from baseline $\geq 15$
Temperature	$<96^{\circ}\text{F}$ ( $<35.6^{\circ}\text{C}$ ) and decrease $\geq 2^{\circ}\text{F}$ ( $\geq 1.1^{\circ}\text{C}$ ) from baseline	$\geq 101^{\circ}\text{F}$ ( $\geq 38.3^{\circ}\text{C}$ ) and increase $\geq 2^{\circ}\text{F}$ ( $\geq 1.1^{\circ}\text{C}$ ) from baseline

Abbreviations: BP = blood pressure; bpm = beats per minute.

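### The SAP's safety displays leave out SpO2 and respiratory rate, list a weight measure that has no follow-up value, and give no grouped by-arm rate of infusion-related and hypersensitivity reactions

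*SAP*

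**What the plan says.** **Vital signs collected.** Protocol 8.2.2 lists six items: temperature, blood pressure, pulse, "respiration rate", "saturation of peripheral oxygen, and" supplemental oxygen details. In Part 1 and the Part 2 Prevention Cohort they are scheduled daily through Day 57. Protocol 9.4.8 says vital signs will be analysed, with categorical measures compared by treatment and continuous measures modelled by MMRM. It excludes no vital sign.

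**Vital signs analysed.** SAP 6.12.7 says: "The measurements analyzed for vital signs and physical characteristics include systolic blood pressure (BP), diastolic BP, pulse, weight, and temperature". The title of Table PYAD.6.10 ends with "Categorical Criteria for Weight and Temperature Changes in Adults", but its four rows are systolic BP, diastolic BP, pulse and temperature. For the first box plot, Table PYAD.6.9 specifies: "Includes participants who have both a baseline and a postbaseline measurement from a planned visit". Its change and shift displays likewise need both values.

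**Risks named.** Protocol 2.3 states: "Additional manageable risks associated with most therapeutic monoclonal antibodies are the potential for infusion-related hypersensitivity and cytokine release reactions". It also describes worsening of COVID-19 within 24 hours of infusion, seen after authorization of LY3819253: "Signs and symptoms may include fever, hypoxia or increased respiratory difficulty".

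**Reactions.** Protocol 8.3.6 asks that "additional details describing each symptom should be provided to the sponsor in the infusion-related reaction/hypersensitivity CRF". Protocol 10.3.3 sends the grading of infusion-related events to section 6.1.1.2, where the DAIDS table has four levels. SAP 6.12.3 tabulates treatment-emergent events by SOC and preferred term, and Table PYAD 6.8 has every adverse event graded mild, moderate or severe. No SAP section mentions the reaction CRF.

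**The concern.** The SAP's vital-sign list does not match what the protocol measures or the risks it names. The two signs closest to hypoxia and respiratory difficulty are not listed, while a measure with no scheduled follow-up value is. For infusion reactions, the sponsor collects symptom-level detail on a dedicated form but plans no output from it. At stake is whether the report can say, from a prespecified analysis, how many participants per arm had any such reaction, when and how severe, and how many had a marked fall in saturation or rise in respiratory rate.

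**Working it through.** No formula or power figure is involved. The check compares what is collected with what is analysed.

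**Step 1: vital signs.**

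| Measure | Protocol 8.2.2 | SAP 6.12.7 list | Row in Table PYAD.6.10 |
|---|---|---|---|
| Temperature | yes | yes | yes |
| Blood pressure | yes | yes | yes (2 rows) |
| Pulse | yes | yes | yes |
| Respiratory rate | yes | no | no |
| SpO2 | yes | no | no |
| Supplemental oxygen / FiO2 | yes | no | no |
| Weight | no | yes | no (title only) |

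The SAP names 3 of the 6 collected items and omits 3.

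**Step 2: scheduled values after baseline.** Weight appears once in each Schedule of Activities: at screening in 1.3.1 and on Day 1 in 1.3.2. Scheduled post-baseline weights are therefore 0 in both. Under 1.3.1, SpO2 and respiratory rate are due daily on Days 2 to 57, or 57 - 2 + 1 = 56 post-baseline days. Under 1.3.2 they are due on Days 8, 29 and 85 and at early termination, with daily hospital records for those admitted.

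**Step 3: can other outputs stand in for SpO2 and respiratory rate?**
- Severity endpoint. Respiratory rate and SpO2 enter protocol Table 1, but that table applies only to SARS-CoV-2-positive participants, and Moderate and Severe require symptoms as well as signs. The key secondary endpoint then counts PCR-detected cases among participants negative at baseline. It cannot show a desaturation in an uninfected participant. SAP 6.10.3.1 has an exploratory version for the Treatment populations, but it is a composite over 21 days and does not isolate the day after infusion.
- Adverse events. Protocol 10.3.1 exempts hypoxemia due to COVID-19 that needs oxygen or ventilatory support, unless the investigator considers it drug-related. Protocol 8.1.2 keeps expected COVID-19 signs and symptoms out of the AE record. Protocol 2.3 says the cause of the post-infusion worsening is unknown, so its appearance in AE tables depends on a causal judgement. A measured value does not.
- General rules. The MMRM rule in SAP 6.1.4 could be applied to SpO2, but it supplies no threshold, and a mean change can hide a few marked falls.

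Part 1 is where this matters most: it enrolled participants before the baseline RT-PCR result was known, has a placebo arm and follows the daily schedule.

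**Step 4: reactions.** SAP 6.12 gives Fisher p-values and odds ratios for percentages, so each preferred term has a by-arm comparison. For symptoms during or within 6 hours of infusion, protocol 8.3.6 only encourages sites to use the two infusion-reaction terms, so some reactions may be recorded under separate symptom terms. Relatedness cannot be relied on to regroup them: SAP 6.12.3 first plans summaries by relationship, then says related events will not be summarised. The life-threatening DAIDS level has no place in the three-level severity table.

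**The case against.** A reader might infer that data on these risks produce no between-arm result at all. The documents do not support that. Reactions recorded as adverse events appear by arm in the TEAE and SAE tables with tests against placebo, and protocol 9.4.6.1 compares overall TEAEs and SAEs. Protocol 8.3.6 and the instruction in 10.3.3 to record a diagnosis rather than its symptoms should bring many acute reactions under common terms. Scattering is therefore possible, not the expected outcome. The pruritus and dyspnea events in protocol 2.3 come from Study PYAB and do not show how this trial's events will be coded.

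Nor do the documents show that a known hypoxia risk was ignored. SAP Version 4 is dated 7 December 2020 and was written for amendment (c). The current protocol updated its risk text in a later amendment and cites data to 31 December 2020, so this may be a version lag. The worsening described concerns people who already had COVID-19, whereas the Prevention analysis populations are RT-PCR negative at baseline.

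There is also partial cover. The SAP list opens with the word include, the general MMRM wording is broad, and the DSMB reviews unblinded AEs and vital signs monthly. All of this stands and reduces the point. It does not supply a named display or criterion for SpO2 and respiratory rate, a grouped reaction rate, or any use of the reaction CRF. For the fourth DAIDS level, the AE form's life-threatening criterion helps, but protocol 10.3.3 pairs it with the three categories for non-infusion events.

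**Conclusion.** The point holds as a modest, inexpensive improvement to the safety outputs. Followed as written, the SAP specifies no vital-sign display or abnormality criterion for SpO2 or respiratory rate. Its evidence on reactions is limited to term-level tables, with no grouped rate and no four-level severity summary. The weight entry is housekeeping: it produces empty displays and changes no inference. Primary and key secondary tests, alpha and sample size are untouched. No numerical effect can be given, because the documents contain no expected reaction or desaturation rates for this trial. The conclusion assumes that SAP Version 4 is the operative plan and that no separate output specification fills the gap.

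**What to change.** **Vital signs.** Delete weight from SAP 6.12.7 and from the title of Table PYAD.6.10. Add SpO2 and respiratory rate to 6.12.7 and Tables PYAD.6.9 and 6.10. Give each a prespecified treatment-emergent criterion that combines a threshold with a change from baseline, as the existing rows do. The Table 1 cut-points (respiratory rate 20 and 30 per minute; SpO2 93% on room air) are a starting reference, but they were written for severity in infected participants, so the clinical team should settle the values. Show SpO2 together with oxygen use. Present results by randomised arm, overall and by baseline RT-PCR status. Do not split by infection after randomisation: the drug is meant to change it, so the split would break the randomised comparison.

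**Reactions.** Add one table to SAP 6.12.3 with the number and percentage of participants per arm with any event on the infusion-related reaction/hypersensitivity CRF, by onset (during or within 6 hours, versus later) and by the four DAIDS grades. Use the SAP's Fisher test and odds ratio against placebo in Part 1 and the Part 2 Prevention Cohort; a risk difference with 95% CI is optional. Restrict the Part 2 comparison explicitly to the Prevention Cohort, because the Part 2 Safety population also contains the Treatment Cohort, which has no placebo arm.

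**Cost.** SAP wording and a few tables from data already collected. Changes in SpO2 and respiratory rate will partly reflect COVID-19, and the text should say so.

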**Table PYAD.6.9. Tables and Figures Produced to Support Vital Signs and Physical Characteristics**

Analysis Type	Analysis Details
Box plots for observed values by visit	
 
Includes participants who have both a baseline and a postbaseline measurement from a planned visit.
 
Unplanned measurements will be excluded.
 
Last baseline will be used.
 
Descriptive summary statistics will be included in a table below the box plot.
 
No inferential statistics.
 

Box plots for change from baseline values by visit	
 
Includes participants who have both a baseline and a postbaseline planned measurement.
 
Unplanned measurements will be excluded.
 
Last baseline will be used.
 
Descriptive summary statistics will be included in a table below the box plot.
 
Change from last baseline to last postbaseline will also be summarized within the box plot of changes (rightmost column), and descriptive summary statistics will be included in a table below the box plot along with a p-value using the ANCOVA model.
 

Scatter plots of baseline-by-maximum values and baseline-by-minimum values	
 
Each study individually and studies combined will be displayed.
 
Includes participants who have both a baseline and postbaseline observation.
 
Unplanned measurements will be included.
 
Lines indicating the reference limits will be included.
 
Max vs Max: Maximum baseline versus maximum postbaseline.
 
Min vs Min: Minimum baseline versus minimum postbaseline.
 

Summary tables for shifts to high/low	
 
Limits provided by the central lab service will be used to define low and high.
 
Normal/high to low: Includes the number and percentage of participants by treatment whose minimum baseline result is normal or high and whose minimum postbaseline result is low. 
 
Denominator equals participants whose minimum baseline result is normal or high and who have at least 1 postbaseline result.
 
 
 
Normal/low to high: Includes the number and percentage of participants by treatment whose maximum baseline result is normal or low and whose maximum postbaseline result is high. 
 
Denominator equals participants whose maximum baseline result is normal or low and who have at least 1 result during the treatment period.
 
 
 
Statistical comparisons will be included.
 

Abbreviations: ANCOVA = anaylsis of covariance; Max = maximum; Min = minimum.

**Table PYAD.6.10. Categorical Criteria for Abnormal Treatment-Emergent Blood Pressure and Pulse Measurement, and Categorical Criteria for Weight and Temperature Changes in Adults**

Parameter	Low	High
Systolic BP (mm Hg) (Supine or sitting – forearm at heart level)	$\leq 90$ and decrease from baseline $\geq 20$	$\geq 129$ and increase from baseline $\geq 20$
Diastolic BP (mm Hg) (Supine or sitting – forearm at heart level)	$\leq 50$ and decrease from baseline $\geq 10$	$\geq 90$ and increase from baseline $\geq 10$
Pulse (bpm) (Supine or sitting)	$<50$ and decrease from baseline $\geq 15$	$>100$ and increase from baseline $\geq 15$
Temperature	$<96^{\circ}\text{F}$ ( $<35.6^{\circ}\text{C}$ ) and decrease $\geq 2^{\circ}\text{F}$ ( $\geq 1.1^{\circ}\text{C}$ ) from baseline	$\geq 101^{\circ}\text{F}$ ( $\geq 38.3^{\circ}\text{C}$ ) and increase $\geq 2^{\circ}\text{F}$ ( $\geq 1.1^{\circ}\text{C}$ ) from baseline

Abbreviations: BP = blood pressure; bpm = beats per minute.

### **6.12.8. Immunogenicity**

If data from validated immunogenicity assays are available, treatment-emergent antidrug antibodies (TE-ADAs) may be assessed.

Treatment-emergent ADAs are defined as participants

- with a 2-fold (1 dilution) increase in titer than the minimum required dilution if no ADAs were detected at baseline (treatment-induced ADA) or
- with a 4-fold (2 dilutions) increase in titer compared with baseline if ADAs were detected at baseline (treatment-boosted ADA).

The frequency and percentage of participants with preexisting ADA and who are TE-ADA positive (TE-ADA+) to each study intervention will be tabulated.

The distribution of titers and frequency of neutralizing antibodies (if assessed) for the TE-ADA+ participants may also be tabulated.

The relationship between the presence of antibodies and PK parameters, efficacy response or safety to each study intervention may also be assessed.

### **6.13. Subgroup Analyses**

This study is not powered for subgroup analyses; therefore, all subgroup analyses will be treated as exploratory.

Subgroup analyses will be conducted for the primary and key secondary endpoints. Subgroups may include

- role within the facility (resident, staff)
- age group by role within the facility (residents  $<$  median resident age, residents  $\geq$  median resident age, staff  $<$  median staff age, staff  $\geq$  median staff age)
- sex (male, female)

- race
- ethnicity
- concomitant medication of interest use (yes/no)

Additionally, AEs, SAEs, and TEAEs will be summarized by role within the facility (resident vs staff).

For subgroup analyses, all tests of interactions between treatment groups and other factors will be conducted at a 2-sided alpha level of 0.10. Treatment group differences will not be evaluated within each category of the subgroup if the interaction is statistically significant. If any group within the subgroup is <10% of the total population, only summaries of the efficacy data will be provided, that is, no inferential testing.

The analysis of additional subgroups and/or subgroup analyses on additional endpoints will not require an amendment to the SAP.

Within each subgroup category the relevant summary measure by treatment, treatment differences (compared to placebo) and 95% CIs will be displayed. Also, p-values using appropriate statistical tests for treatment comparison will be provided. Forest plots may be generated to display the treatment difference and 95% CIs for selected efficacy subgroup analyses.

Concomitant therapies of interest include remdesivir, lopinavir/ritonavir, chloroquine, hydroxychloroquine, anticoagulants, or other investigational interventions. Details of the medications included in this subgroup are provided below in [Table PYAD.6.11](#). Other concomitant therapies of interest may be evaluated based on available external information.

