5.2. Exclusion Criteria

Participants are excluded from the study if any of the following criteria apply:

7. For Parts 1 and 2, recovered from COVID-19 disease or asymptomatic infection
8. For Parts 1 and 2, a prior history of a positive SARS-CoV-2 serology test
9. For Parts 1 and 2, a history of Convalescent COVID-19 plasma treatment
10. Are an inpatient in hospital
11. For Parts 1 and 2, participation in a previous SARS-CoV-2 vaccine trial or received an approved SARS-CoV-2 vaccine
12. For Parts 1 and 2, previous receipt of SAR-CoV-2-specific monoclonal antibodies
13. Have participated, within the last 30 days, in a clinical study involving an investigational product. If the previous investigational product has a long half-life, 5 half-lives or 30 days (whichever is longer) should have passed. This criterion does not apply to products described in Criteria 9, 11, and 12.
14. Are pregnant or breast feeding
15. Are concurrently enrolled in any other type of medical research judged not to be scientifically or medically compatible with this study
16. Have known allergies to related compounds of LY3819253, LY3832479 or any components of the formulation
17. Suspected or proven serious, active bacterial, fungal, viral, or other infection that in the opinion of the investigator could constitute a risk when taking investigational product
18. Have any serious concomitant systemic disease, condition or disorder that, in the opinion of the investigator, should preclude participation in this study.

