6.5. Concomitant Therapy

Concomitant Therapy

Participants should be treated according to standard of care, even as it evolves, and medications may be part of the treatment paradigm.

Remdesivir may be initiated as standard of care for participants requiring hospitalization.

If the local standard of care per written policies or guidelines (that is, not just an individual clinician decision) includes investigational agents to treat COVID-19, then starting these during the study is permitted, but may require additional safety monitoring.

Convalescent COVID-19 plasma treatment is not allowed, except in hospitalized participants.

Vaccines for SARS-CoV-2 should not be used prior to Week 8 of the evaluation period for the prevention cohort of Part 2.

Any medication, investigational agent, or vaccine, including over the counter or prescription medicines, vitamins, and/or herbal supplements, or other specific categories of interest (such as convalescent COVID-19 plasma treatment) that the participant is receiving at the time of enrollment or receives during the study must be recorded along with

- Reason for use
- Dates of administration including start and end dates, and
- Dosage information including dose and frequency for concomitant therapy of special interest.

Acetaminophen and corticosteroid use are permitted at any time during the study.

Other concomitant medication may be considered on a case-by-case basis by the investigator in consultation with the sponsor if required.

The sponsor should be contacted if there are any questions regarding concomitant or prior therapy.

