#### 6.1.1. Analysis Populations

Patient populations are defined in [Table PYAD.6.1](#) along with the analysis they will be used to conduct. The treatment groups and inferential comparisons described in [Table PYAD.6.1](#) will be used unless otherwise specified. Also, unless otherwise specified, for all populations/analysis, patients will be analyzed according to the treatment to which they were assigned.

If enrolling to a placebo-controlled trial is challenged by an effective medication becoming available for prevention of COVID-19 and SARS-CoV-2, then the placebo arm may be dropped in Part 2.

Throughout the document, the term “the Prevention populations” will be used to describe both the Part 1 Prevention and Part 2 Prevention populations. Analyses on the Prevention populations will be conducted on each Prevention population separately. The terms “the Treatment populations” and “the Safety populations” are defined similarly, including those populations from Part 3 of the study.

Table PYAD.6.1. Analysis Populations

Population	Description
Entered	
Definition: All patients who signed informed consent.
 
Purpose: Used for disposition analysis.
 
Treatment Groups: None
 
Inferential Comparisons: None

Enrolled/Intent-to-Treat (ITT)	
Definition: All participants assigned to treatment, regardless of whether they take any doses of study treatment, or if they took the correct treatment. Patients will be analyzed according to the treatment group to which they were assigned.
 
Purpose: Used for disposition, demographic, and safety analyses.
 
Treatment Groups (Short Label):
 
 
Part 1: 4200 mg LY3819253 (4200 LY) and placebo (Pbo)
 
Part 2: 700 mg LY3819253, 350 mg LY3819253 + 700mg LY3832479, and placebo
 
 
Inferential Comparisons: LY versus placebo

Part 1 Prevention	
Definition: All participants in the Enrolled/Intent-to-Treat population in Part 1 who are SARS-CoV-2 RT-PCR negative and serology negative at baseline.
 
Purpose: Used for efficacy and health outcomes analyses.
 
Treatment Groups (Short Label): 4200 mg LY3819253 (4200 LY) and placebo (Pbo)
 
Inferential Comparisons: LY versus placebo

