## 6.9. Prior Medication and Concomitant Therapy

Medications will be classified into anatomical therapeutic chemical (ATC) drug classes using the latest version of the WHO drug dictionary. Medication start and stop dates will be compared to the date of the first dose of treatment to allow medications to be classified as concomitant.

*Prior medications* are those medications that start and stop prior to the date of the first dose of study treatment. *Concomitant medications* are those medications that start before, on, or after the first day of study treatment and continue into the evaluation period. For all summary tables of concomitant medications, Preferred Terms of concomitant medication will be sorted by descending frequency in the LY arm.

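### The exploratory concomitant-medication subgroup counts drugs started after dosing, so membership depends partly on the outcome and its stratum results are distorted

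*SAP*

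**What the plan says.** SAP 6.13 opens its list with "Subgroup analyses will be conducted for the primary and key secondary endpoints. Subgroups may include". The items are role in the facility, age group by role, sex, race, ethnicity and "concomitant medication of interest use (yes/no"). All but the last are fixed before dosing. No time window is attached to the last.

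SAP 6.9 supplies the only definition of the term: concomitant medications "are those medications that start before, on, or after the first day of study treatment and continue into the evaluation period". A drug first given in week 3 therefore counts.

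On which drugs count, SAP 6.13 says: "Concomitant therapies of interest include remdesivir, lopinavir/ritonavir, chloroquine, hydroxychloroquine, anticoagulants, or other investigational interventions". Table PYAD.6.11 adds dexamethasone and baricitinib, and names heparin, fondaparinux and argatroban as anticoagulants.

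On when such drugs are started, Protocol 6.5 says: "Remdesivir may be initiated as standard of care for participants requiring hospitalization". Where written local standard of care "includes investigational agents to treat COVID-19, then starting these during the study is permitted". Protocol 5.2 excludes people who "Are an inpatient in hospital". The Part 1 Prevention population is restricted to participants "who are SARS-CoV-2 RT-PCR negative and serology negative at baseline" (SAP 6.1.1), and the Part 2 definition has the same restriction.

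SAP 6.13 also labels all subgroup work exploratory, tests interactions at two-sided 0.10, displays treatment differences with 95% confidence intervals in each category, allows forest plots, and withholds inferential testing when any category holds under 10% of the population.

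**The concern.** A subgroup contrast keeps the protection of randomization only if membership is settled before treatment can act. Here the population is free of infection at entry and not in hospital. Remdesivir, lopinavir, baricitinib, investigational agents and much dexamethasone use would then mostly begin after a participant falls ill with COVID-19, which is the event being counted. The 'yes' category collects cases and the 'no' category loses them.

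If the antibody also makes illness milder, as Protocol 2.2 expects, active-arm cases may be given these drugs less often than placebo cases. The split would then also depend on treatment. At stake is a row in a subgroup table or forest plot that suggests effect modification by background therapy where none exists, placed beside rows that are valid.

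**Working it through.** **The plan's own figure.** The documents give no number for this subgroup. The planning inputs, from Protocol 9.2 for Part 1, are a placebo 8-week rate of 4.0% for moderate-or-worse COVID-19, risk ratio 0.33, two-sided 0.05, 90% power and about 1300 participants; allocation is 1:1 (Protocol 6.3). Schoenfeld's formula gives 4 × (1.960 + 1.282)² / (ln 0.33)² = 34.2 events, against the stated 33. The gap does not matter here. With 650 per arm, expected cases are 650 × 0.04 = 26 and 26 × 0.33 = 8.58.

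**Assumptions not in the documents.** Let b be the share using a listed drug at baseline, unrelated to outcome (0 to 10%). Let q be the share of cases, among participants not already users, who start a listed drug because of COVID-19 (10 to 60%), by arm.

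**Formulas**, for an arm with risk p:
- 'yes' risk = p[b + (1 − b)q] / {p[b + (1 − b)q] + (1 − p)b}
- 'no' risk = p(1 − q) / {p(1 − q) + (1 − p)}

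**Truth in every stratum:** p = 0.04 and 0.0132; RR 0.33; risk difference −2.7 points; OR = (0.0132/0.9868)/(0.04/0.96) = 0.32.

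**Worked line** (b = 2%, q = 30% placebo, 10% active):
- 'yes', placebo: 0.04 × 0.314 = 0.01256; 0.01256/(0.01256 + 0.0192) = 39.5%.
- 'yes', active: 0.0132 × 0.118 = 0.00156; 0.00156/(0.00156 + 0.01974) = 7.3%. OR 0.12.
- 'no': 0.028/0.988 = 2.83% and 0.01188/0.99868 = 1.19%. RR 0.42, OR 0.41.

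| b | q placebo / active | 'yes' risk, placebo vs active | 'yes' difference (points) | 'yes' OR | 'no' RR | 'no' OR |
|---|---|---|---|---|---|---|
| 0 | 30% / 10% | 100% vs 100% | 0 | undefined | 0.42 | 0.41 |
| 2% | 10% / 10% | 19.7% vs 7.3% | −12.4 | 0.32 | 0.33 | 0.32 |
| 2% | 30% / 30% | 39.5% vs 17.4% | −22.2 | 0.32 | 0.33 | 0.32 |
| 2% | 30% / 10% | 39.5% vs 7.3% | −32.2 | 0.12 | 0.42 | 0.41 |
| 2% | 60% / 30% | 55.9% vs 17.4% | −38.5 | 0.17 | 0.57 | 0.56 |
| 10% | 30% / 10% | 13.4% vs 2.5% | −10.9 | 0.165 | 0.42 | 0.41 |

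Three readings follow.
- Risks and risk differences move whenever q > 0, even with equal use by arm.
- The OR moves only when q differs by arm.
- The direction in the 'yes' stratum depends on b.

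**No true effect** (RR 1, b = 2%, q = 30% / 10%): OR is 0.38 in 'yes' and 1.29 in 'no', an apparent benefit beside an apparent harm.

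**A more frequent endpoint.** At an assumed 10% placebo rate (true OR 0.31), with b = 2% and q = 30% / 10%, the ORs are 0.115 and 0.395, so the pattern persists.

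**The 10% rule.** Users created by the outcome are (0.04 × 0.30 + 0.0132 × 0.10)/2 = 0.67% of participants, about 8.7 of 1300. If every case were treated, the share would be (0.04 + 0.0132)/2 = 2.7%. Reaching 10% then needs baseline use of (0.10 − 0.0266)/(1 − 0.0266) = 7.5%. At q = 30% in both arms it needs (0.10 − 0.00798)/(1 − 0.00798) = 9.3%.

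**Baseline-only definition** (q = 0): both strata return RR 0.33, difference −2.7 points and OR 0.32.

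**The case against.** The best defence is that little hangs on this. The subgroup is optional, exploratory and outside the testing scheme of SAP 6.5. At the planned event rate the 10% rule would withhold p-values and the interaction test unless baseline use reached roughly 7.5 to 9.3%. All of that stands. It does not rescue the summaries, which are still produced, and an exploratory label deals with power and multiplicity rather than with a split made by the outcome. The rule is also not certain to apply. The documents give no baseline use rate, anticoagulants are on the list, and at an assumed 10% placebo rate with every case treated about 3.6% baseline use would suffice.

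A second defence is that the analysis model is logistic, and with equal use among cases the OR is preserved. That also stands. Unequal use is plausible from the expected milder illness, but neither document establishes it.

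A third is that the 4.0% rate belongs to a key secondary endpoint. The documents give no rate for the mild-or-worse primary endpoint. Since remdesivir is tied to hospitalization, the treated share of those broader cases may be smaller, which would shrink the distortion.

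A reader might infer that the 'yes' group is almost all cases and so must show almost no effect. The documents do not support that. Heparin, fondaparinux, argatroban, hydroxychloroquine and dexamethasone are not confined to COVID-19, and 2% baseline users is enough to turn the 'yes' result into an exaggerated benefit.

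**Conclusion.** The point holds for this one subgroup. As written, SAP 6.9 and 6.13 together let post-dosing treatment of COVID-19 define a category in which COVID-19 is then compared between arms. Stratum risks and risk differences are distorted under any non-zero q. Odds ratios and the interaction are distorted as well if use among cases differs by arm.

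The sizes (a 'no' risk ratio near 0.42 instead of 0.33; a 'yes' stratum running from no effect to an odds ratio near 0.12) illustrate assumed use rates and are not forecasts. It would be wrong to infer that the primary or key secondary tests are biased, because none of them uses this split. The change is worth making because it is nearly free, but no confirmatory conclusion depends on it.

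**What to change.** In SAP 6.13, define the category as use of a listed medication that was started before study drug administration and was ongoing on Day 1. If too few participants qualify, drop it as an efficacy subgroup. Show use begun after dosing only in the by-arm concomitant medication tables already planned (SAP 6.9, Table PYAD.6.6).

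The cost is about one sentence. Protocol 6.5 already requires start and end dates, and SAP 6.9 already compares them with the dosing date. Protocol 9.4.7 names only residents versus staff as a subgroup analysis, so nothing promised there is lost. The downside is size: with inpatients excluded and the population free of infection at entry, few baseline users of the COVID-19-specific drugs are expected, and the redefined subgroup may be small.
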